2.1.2 Exclusion Criteria

- a. Women of child-bearing potential who are pregnant or breastfeeding because of the potentially dangerous effects of the treatment on the fetus or infant.
- b. Any form of primary immunodeficiency (such as Severe Combined Immunodeficiency Disease).
- c. Concurrent opportunistic infections. (The experimental treatment being evaluated in this protocol depends on an intact immune system. Patients who have decreased immune

competence may be less responsive to the experimental treatment and more susceptible to its toxicities).

- d. Active systemic infections requiring anti-infective treatment, coagulation disorders or any other active or uncompensated major medical illnesses.
- e. Patients who are receiving any other investigational agents.

2.2 SCREENING EVALUATION

Note: Testing for screening evaluation is conducted under the NCI SB companion protocol, 99-C-0128 (Evaluation for NCI Surgery Branch Clinical Research Protocols).

Note: The date of enrollment is the date the subject signs the written informed consent document. The patient will be consented and enrolled on this protocol once the patient has adequate leukapheresis material banked by the Surgery Branch Cell Production Facility (SB CPF) and prior to administration of the first vaccine.

2.2.1 Within 3 Months Prior to Enrollment

- HIV antibody titer, HBsAg determination, and anti HCV
- Confirmation of diagnosis of metastatic melanoma or epithelial cancer by the Laboratory of Pathology of NCI. (Note: Testing is permitted to be conducted at any time prior to enrollment.)
- Anti CMV antibody titer, HSV serology, and EBV panel. (Note: Patients who are known to be positive do not need to be retested.)

2.2.2 Within 4 Weeks Prior to Enrollment

- Complete history and physical examination. (Note: Patient history may be obtained within 8 weeks prior to enrollment.)
- Baseline imaging to determine the status of disease. This may include CT, MRI, PET, and/or photography.

2.2.3 Within 7 Days Prior to Enrollment

- Physical examination, including ECOG of 0, 1, or 2
- Vital signs
- CBC w/differential
- Acute Care Panel (sodium, potassium, chloride, bicarbonate, creatinine, glucose, BUN), Hepatic Panel (alkaline phosphatase, AST/GOT, ALT/GPT, total bilirubin, direct bilirubin), Mineral Panel (albumin, calcium, magnesium, phosphorus), Uric Acid, Creatinine Kinase, Lactate Dehydrogenase, Total Protein
- PT/PTT
- β -HCG pregnancy test (serum or urine) on all females of child-bearing potential
- Urinalysis, with culture if indicated
- Chest x-ray
- EKG

2.3 REGISTRATION PROCEDURES

2.3.1 Prior to Registration for this Protocol

Patients will initially sign the consent for and enroll on the NCI SB companion protocol, 03-C-0277 (Cell Harvest and Preparation for Surgery Branch Adoptive Cell Therapy Protocols), prior to tumor harvest and leukapheresis for generation of the cell product. Patients will sign the consent for and enroll on this treatment protocol once the patient has adequate leukapheresis material banked by the SB CPF and prior to administration of the first vaccine.

Immature and mature dendritic cells must pass the FACS and sterility or gram stain assay as noted in the Certificates of Analysis (CoAs) ([Appendix 2](#) and [Appendix 3](#)). If cells do not meet CoA requirements then the patient will be taken off-study (Section [3.6.2](#)). Once it is confirmed that immature and mature dendritic cells have met the CoA requirements ([Appendix 2](#) and [Appendix 3](#)), the vaccines will be administered to the patient.

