3.1.2 Treatment Phase

The protocol will consist of two cohorts: cohort 1, patients with melanoma and cohort 2, patients with epithelial cancer.

The study will utilize an optimal design where initially 21 evaluable patients will be enrolled to each cohort. If 0 or 1 of the 21 patients in a given cohort experiences a clinical response, then no further patients will be enrolled; if 2 or more of the first 21 evaluable patients enrolled have a clinical response, then accrual will continue until a total of 41 evaluable patients have been enrolled to that cohort.

Patients will receive no other experimental agents while on this protocol. All patients will receive one course of treatment (4 vaccination cycles). The start date of the course will be the start date of the first vaccination; the end date will be the day of the first post-treatment evaluation (week 8 if the patient receives all 4 cycles).

Enrollment will be staggered within each cohort with three weeks between start dates for the first three patients to allow for a 3-week interval for safety assessment before the next enrolled patient is scheduled to receive their first dose of the DC vaccine.

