3.6.2 Off-Study Criteria

Patients will be taken off study for the following:

- Cells do not meet CoA requirements
- Completed study follow-up period
- Patient requests to be withdrawn from the study
- There is significant noncompliance
- Lost to follow-up
- Investigator discretion
- Progression of disease
- Death

All patients will be co-enrolled on the NCI SB companion protocol, 09-C-0161 (Follow up Protocol for Subjects Previously Enrolled in NCI Surgery Branch Studies). Patients who are taken off-study for progressive disease or study closure on the treatment protocol may be followed on protocol 09-C-0161.

Once a patient is taken off study, no further data can be collected.

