6.3 RESPONSE CRITERIA

For the purposes of this study, patients should be re-evaluated for response approximately two weeks following the last vaccination, then one month later x1, and then every 1-2 months for the first year, and then annually or as clinically indicated. In addition to a baseline scan, confirmatory scans should also be obtained at least 4 weeks following initial documentation of objective response.

Response and progression will be evaluated in this study using the new international criteria proposed by the revised Response Evaluation Criteria in Solid Tumors (RECIST) guideline (version 1.1)¹⁸. Changes in the largest diameter (unidimensional measurement) of the tumor lesions and the shortest diameter in the case of malignant lymph nodes are used in the RECIST criteria.

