11.2 SUBCUTANEOUS INJECTION AND INTRAVENOUS INFUSION PREPARATION

Classification: Peptide Loaded Dendritic Cell Vaccine

Mode of Action: Autologous monocyte derived DC pulsed with peptide neoantigens are recognized in vivo by tumor-specific cytotoxic T-lymphocytes, leading to a major histocompatibility complex-restricted cytotoxic response against tumor cells bearing these neoantigens.

Product Description: The vaccine is derived from autologous DCs produced ex vivo from monocytes isolated from an apheresis product. DCs are produced using clinical grade cytokines (IL-4 and GM-CSF). Neoantigens will be identified from a sequence comparison of a patient's tumor and normal DNA sample. An algorithm will predict mutated sequences with a high probability of binding to a patient's specific HLA repertoire. Neoantigens will be prepared as peptides, either as 25mers, with the mutated amino acid residue situated at position 13, or as minimal epitopes. The patient's tumor infiltrating lymphocytes, cultured from a biopsy sample or PBMC, will be screened for their ability to recognize these predicted neoantigens pulsed onto DCs. Neoantigens recognized by the patient's TIL or PBMC will be used to formulate the vaccine. The vaccine will be formulated for each administration as follows. The identified peptides will be pulsed onto thawed, previously cryopreserved DCs overnight. The following day, the DCs pulsed with peptides will be matured with Poly I:C, R848 and IFN- γ (TLR mix). The DCs will be washed and $1-8 \times 10^7$ will be loaded into syringes for IV and SQ administration.

How Supplied: Neoantigen Peptides: The peptides will be manufactured by Peptides and Elephants (PE) GmBH, Potsdame, Germany. The peptides are supplied as a sterile, GLP grade, lyophilized powder (TFA salt) in vials. Interferon- γ is purchased from Miltenyi as a lyophilized powder. Poly I:C will be purchased from a qualified supplier as a lyophilized powder. R848 will be purchased from a qualified supplier as a lyophilized powder.

Preparation: Peptides for pulsing DCs will be reconstituted in sterile water for DC pulsing to a final concentration of 1 mg/mL. Poly I:C is reconstituted in sterile water at a concentration of 1mg/ml. R848 is reconstituted in sterile water for injection at a concentration of 1mg/mL. Interferon- γ is reconstituted in sterile water for injection at a concentration of 4×10^6 units per mL.

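### Failure of the cell-product certificate is an off-study event with no time limit; read literally, a failure at cycles 2 to 4 could cost a vaccinated patient's response scan.

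*Combined protocol and SAP*

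**What the plan says.** Section 2.3.1 requires immature and mature dendritic cells to pass FACS and sterility or gram stain tests under the certificates of analysis (CoA) in Appendices 2 and 3. It then says "If cells do not meet CoA requirements then the patient will be taken off-study" and points to 3.6.2, where the off-study list contains "Cells do not meet CoA requirements". Neither place gives a time limit. The next sentence in 2.3.1 makes release a condition for dosing: "Once it is confirmed that immature and mature dendritic cells have met the CoA requirements", the vaccines are given.

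Dosing is on Days 0, 14, 28 and 42 (3.2). Section 11.2 says "The vaccine will be formulated for each administration as follows", and describes thawing, pulsing and maturing the cells. Under Appendix 3, viability, cell count, FACS identity, gram stain and endotoxin results are available before infusion. Aerobic culture, anaerobic culture and mycoplasma results come only afterwards.

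On the consequence, 3.6.2 says "Once a patient is taken off study, no further data can be collected". On the companion follow-up protocol it says "Patients who are taken off-study for progressive disease or study closure on the treatment protocol may be followed on protocol 09-C-0161", just after stating that every patient is co-enrolled there. Section 6.1 ends routine adverse-event follow-up at the second follow-up evaluation or at off-study, whichever is earlier.

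On shortened courses, 3.1.2 says of the course of treatment that "the end date will be the day of the first post-treatment evaluation (week 8 if the patient receives all 4 cycles"). Section 6.3 says "patients should be re-evaluated for response approximately two weeks following the last vaccination".

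**The concern.** The primary objective is the response rate in patients who receive the vaccine. A later lot can fail for a manufacturing reason unrelated to the patient's disease. The sensible result is that the dose is not given and the patient is still scanned. As written, the event leads to removal from study. Section 3.6.1, which lists reasons to stop therapy only, does not name product failure; investigator discretion could serve, but it stands in both lists.

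The first response scan, the post-vaccine immune samples and routine adverse-event follow-up of a vaccinated patient are at stake. Losing them would not fit the plan's own expectation, in 3.1.2 and 6.3, that a patient with fewer than four cycles still has a post-treatment assessment.

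**Working it through.** **Timing.** The first follow-up evaluation, with response imaging, is at Day 56 (3.4.1). A failure at cycle 2, 3 or 4 comes 56 − 14 = 42, 56 − 28 = 28 or 56 − 42 = 14 days earlier.

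**Opportunities.** At full accrual a cohort has 41 × 4 = 164 mature lots, of which 41 × 3 = 123 (75%) are tested after the patient's first vaccination. These are occasions for failure, not expected failures.

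**The plan's own design (8.2).** Stop if at most 1 of 21 respond; inadequate if at most 4 of 41 respond; p0 = 0.05, p1 = 0.20. With X1 ~ Bin(21, p) and X2 ~ Bin(20, p):
- Early termination at 5%: P(X1 ≤ 1) = 0.717 (stated 72%).
- Type I error: Σ over x ≥ 2 of P(X1 = x) · P(X2 ≥ 5 − x) at p = 0.05 = 0.046 (limit 0.05).
- Power: the same sum at p = 0.20 = 0.902 (stated 90%).
- Total: 2 × (41 + 2) = 86 (stated 86).

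The design reproduces.

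**Size under assumed failure rates.** The documents give no release-failure rate, so the per-lot rate f is an assumption. Further assumptions are independent lots, every patient reaching cycle 4, each failure leading to removal, and no removed patient being scanned. Together these make the result a worst case for each f. The share of patients with a failure at cycles 2 to 4 is q = 1 − (1 − f)³.

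Two consequences are possible, because the documents define evaluability in two ways:
- Under 6.3.1 an unscanned patient is inevaluable and would be replaced. Design power is then unchanged, but the allowance of 2 inevaluable patients per cohort (8.2) may be exceeded. That means 3 or more among 43 enrolled: P(Bin(43, q) ≥ 3).
- Under 8.3 a patient who received pulsed cells is evaluable. Counted as a non-responder, the response probability becomes 0.20 × (1 − q), and the power sum is repeated at that value.

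| Assumed f | q | Expected among 41 (41q) | P(more than 2 of 43) | 0.20 × (1 − q) | Power |
|---|---|---|---|---|---|
| 0.5% | 1.5% | 0.6 | 2.6% | 0.197 | 89.4% |
| 1% | 3.0% | 1.2 | 13.5% | 0.194 | 88.7% |
| 2% | 5.9% | 2.4 | 46.8% | 0.188 | 87.0% |

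Against 90.2%, the worst-case power loss is 0.8, 1.5 and 3.2 percentage points on the rounded figures. The disagreement between 6.3.1 and 8.3 exists apart from this rule and is used here only to bound its effect.

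**The case against.** The strongest reply is that the sponsor meant a gate before the first dose. The rule sits under a heading about the period before registration, the following sentence releases the vaccines as a series, and the 3.6.2 entry may only restate the same rule. Section 3.1.2, which foresees shortened courses, fits that reading. This is probably right about intent. But 2.3.1 expressly covers mature cells and Appendix 3, that product is made for each dose, and 3.6.2 stands as a general list, so the text does not say it.

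Second, a reader might infer that removal would necessarily come before the response scan. The documents do not support that. Section 3.6 asks, before removal from study, for effort to have all subjects complete a safety visit about 30 days after the Day 56 evaluation. If that succeeds, the Day 56 imaging has passed, and the visit falls at about the time of the second follow-up evaluation. It remains an effort clause and does not itself mention a scan, so it reduces the risk without removing it.

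Third, the rule speaks of cells, not of any single lot. Doses come from cryopreserved cells and cycles 2 to 4 have ±5-day windows, so a replacement dose is neither provided for nor excluded. That would lower the numbers above.

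Fourth, safety data would not all stop. Serious-event reporting under 7.3 has no off-study cut-off, and 6.1 also says events are followed to baseline or stabilization. All patients are co-enrolled on 09-C-0161, although the sentence on follow-up there names only progression and study closure, and what it collects cannot be seen from these documents.

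**Conclusion.** The point holds in a limited form and is minor. The off-study rule has no time limit while the product is released anew for each dose, so a literal reading could cost a vaccinated patient's scan, immune samples and routine adverse-event follow-up if the 3.6 visit does not happen first.

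Two stronger inferences are not supported. One is that the primary analysis is materially threatened: no failure rate is given, and at assumed rates up to 2% per lot worst-case power stays at 87.0% or above, so the average effect is probably small. The allowance for inevaluable patients is more sensitive (up to 46.8% at a 2% rate), but only if no removed patient is scanned. The other is that a late positive culture or mycoplasma result also forces removal. The text is ambiguous there, but since vaccine is given once requirements are met, the coherent reading is that only pre-infusion release tests count.

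**What to change.** In 2.3.1 and 3.6.2, limit the off-study consequence to CoA failure before the first vaccination. Add that after a failure at a later cycle that dose is not given; a replacement dose or stopping therapy is at the investigator's discretion; and the patient stays on study for the first post-treatment imaging, the immune samples, and adverse-event follow-up to the second follow-up evaluation. With that limit, a culture or mycoplasma result that arrives after infusion no longer raises the question of removal from study.

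The change should not make every later failure a mandatory reason to stop therapy. That would be a new stopping rule and would bar a replacement dose.

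The cost is an amendment of wording. Already planned visits and scans continue for a few partly treated patients, and including them may slightly lower the reported response rate.

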2.3.2 Registration Procedure

Authorized staff must register an eligible candidate with NCI Central Registration Office (CRO) within 24 hours of signing consent. A registration Eligibility Checklist from the web site (<http://home.ccr.cancer.gov/intra/eligibility/welcome.htm>) must be completed and sent via encrypted email to: NCI Central Registration Office at [contact]. After confirmation of eligibility at Central Registration Office, CRO staff will call pharmacy to advise them of the acceptance of the patient on the protocol prior to the release of any investigational agents. Verification of Registration will be forwarded electronically via email to the research team. A recorder is available during non-working hours.

2.4 TREATMENT ASSIGNMENT PROCEDURES

2.4.1 Cohorts

Subjects will be enrolled in one of two cohorts:

Number	Name	Description
1	Melanoma	Patients with metastatic melanoma
2	Epithelial	Patients with epithelial cancer

2.4.2 Arms

Number	Name	Description
1	Experimental Therapy	Peptide loaded dendritic cell vaccine on days 0, 14, 28, and 42

2.4.3 Randomization and Arm Assignment

[figure not shown]
This is a non-randomized study. All subjects will be directly assigned based on cohort as follows:

- Subjects in Cohorts 1-2 will be directly assigned to Arm 1.

3 STUDY IMPLEMENTATION

3.1 STUDY DESIGN

3.1.1 Pre-Treatment Phase: DC Preparation

Under 03-C-0277, patients with evaluable metastatic melanoma or epithelial cancers will undergo resection of the tumor and apheresis. Whole exome and RNA sequencing will be performed to identify all cancer mutations using our standard procedures. TIL will be grown and expanded for this trial according to standard operating procedures submitted in the IND. After a sufficient yield of TIL (5×10^7 cells) is expanded and PBMCs are available, immunogenic neoantigens will be identified by high throughput immunologic screening using long peptides and tandem minigenes covering all mutated epitopes to identify the exact mutations recognized by autologous T cells. For vaccine preparation, patients will undergo apheresis and DCs will be produced and cryopreserved for vaccine preparation. Peptides (15-25mers with the mutation at positions 13) or minimal epitopes (9-10mers) will be synthesized and pulsed on autologous antigen presenting cells (DC). The antigen pulsed DC will then be matured using a TLR mix.

Patients will receive peptide-loaded mature dendritic cells intravenously and subcutaneously at biweekly intervals for 4 cycles. Immunologic tests will be performed as described in Section 5.5.

3.1.2 Treatment Phase

The protocol will consist of two cohorts: cohort 1, patients with melanoma and cohort 2, patients with epithelial cancer.

The study will utilize an optimal design where initially 21 evaluable patients will be enrolled to each cohort. If 0 or 1 of the 21 patients in a given cohort experiences a clinical response, then no further patients will be enrolled; if 2 or more of the first 21 evaluable patients enrolled have a clinical response, then accrual will continue until a total of 41 evaluable patients have been enrolled to that cohort.

Patients will receive no other experimental agents while on this protocol. All patients will receive one course of treatment (4 vaccination cycles). The start date of the course will be the start date of the first vaccination; the end date will be the day of the first post-treatment evaluation (week 8 if the patient receives all 4 cycles).

Enrollment will be staggered within each cohort with three weeks between start dates for the first three patients to allow for a 3-week interval for safety assessment before the next enrolled patient is scheduled to receive their first dose of the DC vaccine.

3.1.3 Protocol Stopping Rules

New subject enrollment to the protocol will be temporarily halted if any of the following conditions are met, and discussions will be had with the FDA or NIH IRB regarding protocol revisions if applicable:

- If one or more treatment-related death occurs due to vaccination, we will promptly discuss this with the NCI IRB and the FDA.
- Two or more patients develop a grade 3 or greater toxicity at any point in the study not attributable to disease progression (or circumstances unrelated to the study).
 - The following grade 3 reactions commonly associated with immunization **will not** be included in this protocol stopping rule:
 - Pruritus/itching: intense or widespread and interfering with ADL lasting <72 hours
 - Fatigue: severe fatigue interfering with ADL lasting < 72 hours
 - Fever: > 40.0°C for < 24 hours
 - Local lymphadenopathy lasting < 1 week
- If one of the first three patients (or 2 of the first 6 patients, or 3 of the first 9 patients, or 4 of the first 12 patients) develop grade 3 autoimmunity, that cannot be resolved to less than or equal to a grade 2 autoimmune toxicity within 10 days, or any grade 4 or greater autoimmune toxicity.

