3.3 ON-STUDY EVALUATION

3.3.1 Within 7 Days Prior to the 1st Vaccination (Day 0)

- Repeat all screening procedures from Section **2.2.3** if not completed within 7 days prior to the 1st vaccination (Day 0).

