3.5 STUDY CALENDAR

Assessments	Screening/Baseline (prior to enrollment on treatment protocol)			On-Study/Course of Treatment (1 vaccine = 1 cycle)			Post-Treatment Follow-up		
	Within 3 Months	Within 4 Weeks	Within 7 Days	Day 0 ¹	Day 14 (±5 d)	Day 28 (±5 d)	Day 42 (±5 d)	Day 56 (±5 d)	Subsequent Follow-up Visits ²
Informed consent ³									
Confirmation of diagnosis by NCI Lab of Pathology ⁴	X								
Medical history ⁵	X								
Physical exam	X			X	X	X	X	X	X
Performance score (ECOG) ⁶				X	X	X	X	X	X
Vital signs ⁷				X	X	X	X	X	X
β-HCG pregnancy test ⁸				X	X	X	X	X	X
Urinalysis ⁹				X	X	X	X	X	X
EKG				X	X				
Toxicity assessment					X	X	X	X	X
Laboratory Procedures									
Viral testing ¹⁰		X							

1 Assessments (except TBNK and research samples) may be done within 7 days prior to the first vaccination on Day 0. **Lymphocyte phenotyping (TBNK) and research samples must be drawn within 2 days prior to the first vaccination on Day 0.**

2 The second follow-up evaluation will take place 1 month (± 5 days) after the first follow-up evaluation (Day 56). Subsequent follow-up evaluations will take place every 1-2 months for the first year, and then annually or as clinically appropriate as determined by the PI. Patients may be seen more frequently as clinically indicated. Patients who are unable or unwilling to return for follow-up evaluations may be followed via phone or email contact. Patients may be asked to send laboratory, imaging and physician exam reports performed by their treating physician.

3 The date of enrollment is the date the subject signs the written informed consent document. The patient will be consented and enrolled on this protocol once the patient has adequate leukapheresis material banked by the SB CPF and prior to administration of the first vaccine.

4 Confirmation of diagnosis of metastatic melanoma or epithelial cancer. Testing is permitted to be conducted at any time prior to enrollment.

5 Patient history may be obtained within 8 weeks prior to enrollment.

6 ECOG of 0, 1, or 2.

7 After each vaccination, vital signs will be monitored hourly (± 15 minutes) for two hours. The post-administration monitoring period may be adjusted by the PI. Complete at all follow-up evaluations within 4 months after the last vaccine.

8 Serum or urine; on all females of child-bearing potential.

9 With culture if indicated.

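### The safety halt in 3.1.3 stops new enrollment only, so it does not cover the first dose of a patient who has consented but not yet been vaccinated

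*Combined protocol and SAP*

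**What the plan says.** Section 3.1.3 states the consequence of a safety trigger: "New subject enrollment to the protocol will be temporarily halted if any of the following conditions are met". The triggers are a treatment-related death; two or more patients with toxicity of grade 3 or worse not explained by progression or unrelated circumstances, with listed exceptions; and a count-based rule for autoimmune toxicity that starts at one of the first three patients. Discussion with the FDA or the IRB follows. The section does not mention vaccination, whether first or later.

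Section 2.2 defines the operative word: "The date of enrollment is the date the subject signs the written informed consent document". Footnote 3 of the study calendar (3.5) repeats this and fixes the timing: "The patient will be consented and enrolled on this protocol once the patient has adequate leukapheresis material banked by the SB CPF", and before the first vaccine. Section 2.3.1 gives the same order of events.

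Section 3.1.2 describes the early stagger: "Enrollment will be staggered within each cohort with three weeks between start dates for the first three patients". Its purpose is a safety assessment "before the next enrolled patient is scheduled to receive their first dose of the DC vaccine". It also says: "The start date of the course will be the start date of the first vaccination".

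Section 3.3.1 has the 7-day screening tests repeated "if not completed within 7 days prior to the 1st vaccination (Day 0". Section 2.3.1 says that once the immature and mature cells meet their certificates of analysis, the patient is given the vaccine.

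**The concern.** A trial-level halt exists so that nobody newly begins the agent while a serious event is being assessed. A patient who has consented but not been dosed has had exactly as much vaccine as a patient who has not yet signed: none. The rule protects the second and, read with the protocol's own definition, not the first.

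At stake is whether a first vaccination could go ahead, in compliance with the protocol, while a treatment-related death or a grade 4 autoimmune toxicity is under discussion. That decision should be fixed in advance in the stopping rule.

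**Working it through.** The plan gives no figure for this rule, so the main check is textual.

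**1. What the halt reaches.** The halt acts on new enrollment (3.1.3). Enrollment is the date of consent (2.2; 3.5, footnote 3). Consent precedes the first vaccine (2.2, 2.3.1). A consented, undosed patient is therefore no longer a new enrollment, and the halt does not reach that patient.

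**2. Whether such patients are foreseen.** They are. Section 3.1.2 speaks of an enrolled patient awaiting a first dose. Section 3.3.1 provides for tests that have gone out of window by Day 0. Sections 2.3.1 and 3.6.2 take a patient off study if the cells fail release. These passages show that an interval exists but not how long it is.

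**3. Whether another section supplies the hold.**

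| Section | What it does | Requires a hold on the first dose? |
|---|---|---|
| 2.3.1 | Product release; dosing follows once the cells pass | No |
| 2.3.2 | Registration is confirmed to pharmacy before agent release | No; this patient may already have passed that step |
| 3.1.2 | Three-week spacing, first three patients per cohort | No; it is a fixed interval not tied to a trigger |
| 3.6.1, 3.6.2 | Removal criteria, including investigator discretion | No; permissive |
| 7.3, 7.5.1 | Event reporting and per-patient review | No |
| Appendix 1, step 2 | Physician orders verified before infusion | No; an order can be withheld but need not be |

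**4. Size, as illustration only.** Inputs: accrual of 1 to 2 patients per month (8.2). The gap from consent to Day 0 is an assumption. The values used are 2 days (suggested by the overnight pulsing in 11.2), 7 days (the test window) and 28 days (an outer value). Section 6.3.3 allows a baseline scan no more than 4 weeks before treatment, so without repeat imaging the oldest permissible scan at consent is 28 minus the gap: 26, 21 and 0 days old respectively.

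Expected consented but undosed patients = rate × gap / 30.4 days per month. The chance that at least one exists at a given moment = 1 − exp(−expected), assuming Poisson accrual.

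- 2 days: 1 × 2/30.4 = 0.066 to 2 × 2/30.4 = 0.132; chance 6% to 12%.
- 7 days: 1 × 7/30.4 = 0.230 to 2 × 7/30.4 = 0.461; chance 21% to 37%.
- 28 days: 1 × 28/30.4 = 0.921 to 2 × 28/30.4 = 1.842; chance 60% to 84%.

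At the average rate implied by 86 patients in 6 years (86/72 = 1.19 per month), the expected numbers are 0.08, 0.27 and 1.10.

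The spread comes almost entirely from the assumed gap. The figures count patients who could be in this state if a trigger occurred. They do not estimate whether a trigger occurs or whether anyone would then be dosed.

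**5. Design figures.** The two-stage rule in 8.2 (stop at 1 or fewer of 21; 5 or more of 41 needed) reproduces: early termination under 5% is 0.717 (stated 72%), type I error is 0.046 and power at 20% is 0.902. None of these depends on the halt.

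**The case against.** The best case against the point is that nobody would give the dose. All vaccinations take place at one center (3.2). Non-progression deaths reach the sponsor within 24 hours and other serious events within one business day (7.3). The investigator reviews each patient's events and reports safety concerns to the IRB immediately (7.5.1). Every infusion needs verified orders for the cells and the date (Appendix 1). No section sets a maximum interval from consent to Day 0, so postponing breaches no stated limit, and 3.3.1 already allows for a later Day 0. For the first three patients in each cohort, the stagger adds time when the strictest autoimmunity trigger applies. All of this stands and keeps the point small. It does not remove it, because each of these controls allows a hold and none requires one.

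A second objection is that the triggers include less grave events. Two grade 3 toxicities at any time, among up to 86 patients with refractory disease, would also hold first doses. That is true, but the rule already stops enrollment on those events, and the undosed enrolled patient is in the same position.

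A reader might infer that the protocol uses enrollment in two senses, consent in 2.2 and first vaccination in 3.1.2, so that the halt is ambiguous. The documents do not support this. Section 3.1.2 spaces start dates and refers to the next enrolled patient as someone still awaiting a dose, which fits the consent definition. The problem is a narrow scope rather than an unclear term.

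**Conclusion.** The point holds as a gap in scope. By the protocol's own definition, the halt in 3.1.3 omits patients who have consented but not been vaccinated, and nothing else makes a hold on their first dose mandatory. It is minor: few patients are likely to be in that state, and existing controls make inadvertent dosing unlikely. The number cannot be estimated from the documents; the illustrative range of about 0.07 to 1.8 patients at any time rests on assumed gaps of 2 to 28 days.

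Two stronger conclusions are tempting and should not be drawn. One is to take the chance that such a patient exists as the risk of a first dose during a review; the documents give no basis for the chance that dosing would proceed. The other is that the halt should also stop patients in mid-course. They are already exposed, so continuing is a separate benefit-risk decision that this finding does not address.

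**What to change.** Add to 3.1.3: *While enrollment is halted, the first vaccination of any enrolled but not yet vaccinated patient is also held, and resumes when enrollment resumes. This sentence does not determine whether patients who have begun vaccination continue.*

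Tying the hold to the resumption of enrollment matters. A hold until IRB or FDA review is complete would add a restart condition that 3.1.3 does not contain. The second sentence prevents silence on cycles 2 to 4 from being read as permission to continue.

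The cost is a few delayed first doses in patients with refractory metastatic cancer. The 7-day tests may need repeating (3.3.1), as may baseline imaging if Day 0 moves more than 4 weeks from the scan (6.3.3). A held patient may progress and come off study undosed (3.6.2), which could use one of the two inevaluable places allowed per cohort (8.2). The required number of evaluable patients and the error rates do not change.
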